3.3.3 Withdrawal

All participants will be notified during the consenting process that they are free to withdraw from the trial at any time, without giving a reason.

Participants will be withdrawn from the trial by the Principal Investigator if:

- 1. The participant develops a medical condition or becomes pregnant either prior to entering the study or during, which may adversely affect the outcome of the study.
- 2. It is clearly demonstrated that the participant is non-compliant completing study activities and the control procedures requested of them.
- 3. A participant suffers an adverse event, which will be reviewed and recorded at each visit and at each phone call, following the immediate discontinuation of the participant during the visit, if necessary.

All data prior to subject withdrawal will be used in analysis; unless the participant specifically requests that their data is not to be used. Withdrawn participants will not be replaced as an anticipated drop-out rate of 20% has been accounted for in the recruitment targets.

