3.0 Experimental Design

Two controlled, randomized, double-blind clinical trials will be developed and undertaken (one in Brazil and the other in the UK) with an intervention period of 12 weeks.

A questionnaire to screen for the relevant inclusion and exclusion criteria (see section A) will be administered in order to select 80 Brazilian female subjects, aged 20 to 59 years, in each of the two countries. The women selected will be randomly divided into two groups: Placebo Group and Supplemented Group, the latter will receive 600UI UI of vitamin D.

The first clinical trial will run in the UK from October 2016 to March 2017 (autumn-winter) and then the second will run in Brazil from April 2017 to September 2017 (autumn-winter). After the analysis of the effect of vitamin D supplementation compared to placebo, the results obtained in the supplemented group will also be analysed according to the genotypes for SNPs in the VDR gene.

We have chosen 12 weeks (3 months) as the supplementation period as we consider this to be ample time for 25OHD levels to rise (half-life of 25OHD is 3 weeks) and this has been demonstrated to be an effective timeframe for supplementation of vitamin D in previous studies.

We have chosen 600IU to enable the study to be relevant to the new IOM US recommendations for vitamin D, which are currently the reference document used in Brazil, even though the Brazilian nutritional table remains with the daily intake recommendation of 200 IU, which was the IOM recommendation in 1997. Compliance will be checked by compliance interviews during the trial and by empty packaging count.

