4.0 Trial Procedures

4.1 Trial visit activities

During this study the subjects will be asked to visit the Clinical Investigation Unit, FHMS, University of Surrey in the UK or the Research Clinic, Faculty of Nutrition, Federal University of Goias in Brazil, on two occasions, at the beginning of the study for baseline measurements and at the conclusion of the study.

We will examine four to eight fasted subjects per study morning.

Trial visits will last approximately 45-60 minutes each and take place in the morning (7am-11am). Participants will be offered refreshments at the end of their appointment.

Consenting and Screening

If participants wish to be screened for participation in the study, they will receive the Participant Information Sheet and then be checked against the study inclusion and exclusion criteria using the 'Screening Questionnaire' (Section A), to be administered by a member of the D-SOL Research Team by phone or self-reported by email.

Baseline visit

If eligible, participants will be invited for the baseline visit. At this visit, they will first be given time to discuss the Participant Information Sheet and any questions they may have regarding the study.

Informed consent will be discussed and participants will be asked to sign the consent form, and will be offered a copy to keep for themselves.

- Health and Lifestyle questionnaire to be administered by a member of the D-SOL Research Team.
- Anthropometrics and blood pressure measured, and fasted blood sample taken (serum 25OHD levels, 1,25-dihydroxy vitamin D, serum calcium, albumin, parathyroid hormone, C-terminal telopeptide (CTX) ≈25ml) with an additional ≈10 ml for genetic profiling and ≈15 for storage for future measurements of nutritional markers.
- pQCT scan of the non-dominant forearm for UK trial or DEXA scan for Brazil trial.
- Bioelectrical impedance analysis (BIA) for body composition.
- Provision of randomly assigned daily supplement (30 days' supply), food diaries and dosimeter (to be returned via SAE provided) and sunlight exposure diary to be returned at 12 week visit. Follow-up appointment details arranged (including interim visit telephone appointments and for re-supply of supplement).

Final visit

- Final adverse event/compliance interview completed with investigator.
- Daily outdoor exposure diary received from participant and check for consistency at visit.

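### Section 3.3.3 withdraws women from the trial rather than only from the supplement, so a randomised woman withdrawn before week 12 has no outcome 25OHD; inviting her to the scheduled final sample is a cheap improvement

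*Combined protocol and SAP*

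**What the plan says.** Section 3.3.3 (Withdrawal) states: "Participants will be withdrawn from the trial by the Principal Investigator if" any of three things happens. The first is a medical condition or pregnancy, before entry or during the study, that may affect the outcome. The second is: "It is clearly demonstrated that the participant is non-compliant completing study activities and the control procedures requested of them". The third is an adverse event, with "following the immediate discontinuation of the participant during the visit, if necessary". The section adds "All data prior to subject withdrawal will be used in analysis", unless the woman asks otherwise, and says that withdrawn women are not replaced because a 20% drop-out allowance is built in.

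Section 4.1 has women attend "on two occasions, at the beginning of the study for baseline measurements and at the conclusion of the study", and blood for 25OHD is listed at those two visits only. Between them come fortnightly telephone calls about adverse events and compliance, and contacts described as "including interim visit telephone appointments and for re-supply of supplement". Section 3.0 adds: "Compliance will be checked by compliance interviews during the trial and by empty packaging count".

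Section 7.0 compares supplemented and placebo women by t test or Mann-Whitney test. It names no analysis population and no method for missing outcomes.

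**The concern.** Non-compliance, intercurrent illness, pregnancy and adverse events can all arise after randomisation. If they end follow-up, the women who remain are no longer exactly the groups that randomisation formed. The comparison by assigned arm is the one that randomisation protects, and it cannot be recovered for a woman whose week-12 blood was never taken. Her data before withdrawal contain a baseline 25OHD and no outcome.

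The stake is choice of analysis. With the week-12 sample, the sponsor can report both the effect by assignment and the effect in women who complied. Without it, only the second is available for the women concerned. The first is relevant because section 1.0 says the data should inform dietary recommendations.

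**Working it through.** **1. Can a withdrawn woman have an outcome?** 25OHD samples: one at baseline, one at the final visit, none between. Withdrawal before the final visit therefore leaves 0 post-baseline values. The risk statement in section 5.0 mentions a screening blood sample, but section 4.1 screens by phone or email, and screening precedes baseline in any case.

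**2. Can withdrawal happen before week 12?** Yes. Fortnightly calls fall at weeks 2, 4, 6, 8 and 10, so there are 5 occasions. A 30-day supply over 84 days (84/30 = 2.8) also implies 2 re-supplies, if each is again 30 days (assumption).

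**3. Who is not affected?** Women whose condition or pregnancy arose before randomisation, and women whose non-compliance or adverse event is acted on at the final visit, if the blood has been drawn. The diary check and final interview both take place at that visit.

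**4. Inputs for size.** From section 3.1: 40 per arm, 0.6 SD, 90% power, 20% drop-out. That power does not reproduce: 40 × 0.8 = 32 per arm gives 65.6% (two-sided 5% t test), and all 40 give 75.5%. This is a separate matter; I use only the 0.6 SD and the 40 per arm. The documents give no withdrawal rate for these reasons. I assume a share f of 5% to 10%, equal in both arms: 2 to 4 of 40 per arm, 4 to 8 of 80 per trial.

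**5. Share of effect kept (r) by a woman who stops.** Section 3.0 gives a 3-week half-life. Under a first-order model (assumption), stopping at week s leaves r = (1 − 2^(−s/3)) × 2^(−(12−s)/3) / (1 − 2^(−4)).
- s = 6: 0.75 × 0.25 / 0.9375 = 0.20
- s = 9: 0.875 × 0.5 / 0.9375 = 0.47
- s = 10: about 0.60

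**6. By-assignment effect and power.** Effect = 0.6 × (1 − f(1 − r)). Gap = 0.6/effect − 1. Power is for a two-sided 5% t test (noncentral t; the plan does not state sidedness).

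| f | r | Effect (SD) | Gap | Power, all 40 per arm | Power, stayers at 0.6 SD |
|---|---|---|---|---|---|
| 5% | 0 | 0.570 | 5.3% | 71.1% | 73.3% (38 per arm) |
| 5% | 0.47 | 0.584 | 2.7% | 73.2% | 73.3% |
| 10% | 0 | 0.540 | 11.1% | 66.5% | 70.9% (36 per arm) |
| 10% | 0.47 | 0.568 | 5.6% | 70.8% | 70.9% |

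The gap is the distance between two estimands. It is not a measured bias.

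**7. Between-arm selection.** Shift = (fS − fP) × d, where fS and fP are the shares withdrawn from the supplemented and placebo arms, and d is the stayers' mean minus the withdrawn women's mean. Equal shares give 0. With 10% against 5% and d = 0.5 SD (assumptions), the shift is 0.05 × 0.5 = 0.025 SD, or 4.2% of 0.6 SD. The sign reverses if the shares or d reverse. The standard error of the difference with 36 and 38 women is √(1/36 + 1/38) = 0.233 SD, so this shift is about 0.11 standard errors.

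**The case against.** The strongest reply is that the plan never claims a by-assignment analysis. Its primary objective, several hypotheses and the good-against-poor responder work concern biological response in women who take the supplement. For a 12-week biomarker trial, a comparison in women who followed the regimen is defensible. That stands as a reason to keep a compliant-only analysis. It is not a reason to forgo the sample, since the sample permits both analyses.

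A second reply is that section 3.0 provides for this: "Two controlled, randomized, double-blind clinical trials will be developed and undertaken". Blinding makes similar withdrawal in the two arms plausible, and the between-arm shift is then zero. This stands. A reader might infer that the rule biases the result in favour of vitamin D; the documents do not support that, because they give neither withdrawal rates by arm nor any direction. Blinding does not, however, close the gap between the two estimands in step 6.

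A third reply is that the fix may bring little. Women withdrawn for not completing study activities may well decline a fasted morning visit, so all 40 per arm is an upper limit. This also stands. A reader might also expect a power gain, because 40 per arm at the full 0.6 SD gives 75.5%. That needs women who stop to keep the whole effect, which does not fit the plan's own 3-week half-life.

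Finally, the 20% allowance addresses how many women are missing, not which ones.

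**Conclusion.** The point holds as a cheap improvement to consider. The text is clear: withdrawal is from the trial, 25OHD is drawn only at the two ends, and nothing elsewhere provides an outcome for a randomised woman withdrawn in between. How often this would happen, and what it would do to the estimate, cannot be known from the documents.

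Under the assumed 5% to 10% withdrawal, equal in both arms, with 0% to about 47% of the effect kept, the effect in stayers exceeds the by-assignment effect by roughly 3% to 11%. Between-arm bias may be zero and is small in the illustrative case.

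A reader might put the whole 20% allowance through the same formula and quote a 25% gap (0.6/0.48 − 1). That is not supported: the allowance covers drop-out of every kind, including women who simply leave.

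**What to change.** In section 3.3.3, separate stopping the supplement from leaving follow-up, with the reasons for stopping unchanged. Invite every randomised woman to the already scheduled week-12 25OHD sample, unless she withdraws consent or the investigator judges the visit medically unsuitable.

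In section 7.0, make the primary supplemented-placebo comparison by randomised arm in all women with a week-12 value. Add a compliant-only analysis as sensitivity, with its compliance threshold fixed before unblinding.

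The cost is wording in two sections and at most about 4 to 8 extra final visits per trial under the assumed rate; some women will decline. Power for the by-assignment comparison is usually slightly lower than in stayers alone: about 71% to 73% against 73.3% at 5% withdrawn, and about 66% to 71% against 70.9% at 10%. Women who withdraw consent or decline stay missing, so the by-assignment comparison is only partly restored.

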4.0 Trial Procedures

4.1 Trial visit activities

During this study the subjects will be asked to visit the Clinical Investigation Unit, FHMS, University of Surrey in the UK or the Research Clinic, Faculty of Nutrition, Federal University of Goias in Brazil, on two occasions, at the beginning of the study for baseline measurements and at the conclusion of the study.

We will examine four to eight fasted subjects per study morning.

Trial visits will last approximately 45-60 minutes each and take place in the morning (7am-11am). Participants will be offered refreshments at the end of their appointment.

Consenting and Screening

If participants wish to be screened for participation in the study, they will receive the Participant Information Sheet and then be checked against the study inclusion and exclusion criteria using the 'Screening Questionnaire' (Section A), to be administered by a member of the D-SOL Research Team by phone or self-reported by email.

Baseline visit

If eligible, participants will be invited for the baseline visit. At this visit, they will first be given time to discuss the Participant Information Sheet and any questions they may have regarding the study.

Informed consent will be discussed and participants will be asked to sign the consent form, and will be offered a copy to keep for themselves.

- Health and Lifestyle questionnaire to be administered by a member of the D-SOL Research Team.
- Anthropometrics and blood pressure measured, and fasted blood sample taken (serum 25OHD levels, 1,25-dihydroxy vitamin D, serum calcium, albumin, parathyroid hormone, C-terminal telopeptide (CTX) ≈25ml) with an additional ≈10 ml for genetic profiling and ≈15 for storage for future measurements of nutritional markers.
- pQCT scan of the non-dominant forearm for UK trial or DEXA scan for Brazil trial.
- Bioelectrical impedance analysis (BIA) for body composition.
- Provision of randomly assigned daily supplement (30 days' supply), food diaries and dosimeter (to be returned via SAE provided) and sunlight exposure diary to be returned at 12 week visit. Follow-up appointment details arranged (including interim visit telephone appointments and for re-supply of supplement).

Final visit

- Final adverse event/compliance interview completed with investigator.
- Daily outdoor exposure diary received from participant and check for consistency at visit.
- Anthropometrics and blood pressure measured, and blood sample taken (serum 25OHD levels, 1,25-dihydroxy vitamin D, serum calcium, albumin, parathyroid hormone, C-terminal telopeptide (CTX) ≈25ml) with an additional ≈10 ml for genetic profiling and ≈15 for storage for future measurements of nutritional markers.
- Bioelectrical impedance analysis (BIA) for body composition.
- Dosimeter and 4-day food diary received from participant (sent to participant prior to appointment).

DNA profiling procedure - After 12 weeks RCT

• Selection of 48 participant samples encompassing the best and worst supplementation-responders in each group, subject to previous consent form participant. Vitamin D related genes will be genotyped in DNA isolated from the study blood samples, DNA will be extracted and vitamin D polymorphisms will be determined by University of Surrey's genetic labs.

A trained phlebotomist will take the blood samples required as part of the trial protocol. Medical cover will be available at all times.

Throughout the duration of the trial, the participants will be contacted via telephone on a fortnightly basis to discuss any issues with any adverse event and compliance and to maintain good communication with the participants. (Please see AE reporting form). In the case of a serious adverse event (SAE) this will be recorded (please see SAE reporting form) and we will report it to both the Sponsor (University of Surrey) and the Surrey Ethics Committee.

The final interview will be completed at the final study visit. Participants have also be asked to return any supplements that were missed to confirm compliance.

For University of Surrey participants: A peripheral quantitative computed tomography (pQCT) scan was performed on the participant's non-dominant forearm at the baseline visit, to measure volumetric bone mineral density at the 4% and 66% radial site. This will allow for separate measurements of trabecular vBMD and trabecular area (4% site) and cortical vBMD and cortical area (66% site), as well as strength strain index, a measure of bone strength. pQCT also measures bone geometry alongside bone density. Therefore the muscle cross sectional area can be determined, which is a measure of muscle force, to which bone strength is adapted to. One scan was performed at baseline only and effective exposure doses were between ~1.5-1.8uSv.

For Federal University of Goiás participants: Body composition (absolute and relative amount of lean and fat mass), whole body mineral density and lower spine and femur bone mineral density was measured with the use of DEXA (located at the Nutrition Clinic based at the Federal University of Goias), at baseline only. Two scans were performed at baseline for each participant: one to assess the whole body mineral density and body composition, and the other to specifically assess fracture risk by scanning the spine and femoral head. Effective exposure doses for theses scans are ~8uSv and ~4uSv respectively.

Results of the body composition, vitamin D status and dietary intake from the self-reported food diaries will be made available to the subjects upon request. The results from the blood analysis will be reported to the subject if there are any health concerns raised. If the results are within healthy ranges the participants will not be contacted unless they specifically request for this information. The investigators will not be contacting their GPs if there are any concerns raised in the study however we will stress that they should contact their GP themselves to discuss the results we found.

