2.0 Objectives & Design

2.1 Primary Objectives: To examine the response (in vitamin D status) to vitamin D supplementation and sunlight exposure, and its influencing factors within and between Brazilian female adults living in the UK and Brazilian female adults living in Brazil.

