3.1 Sample Size and randomisation

A total of 80 subjects (at 90% power) are required for recruitment into the 600 IU vitamin D group vs placebo group for the RCT to be conducted in the UK and a total of 80 subjects (at 90% power) are required for recruitment into the 600 IU vitamin D group vs. placebo group for the RCT to be conducted in Brazil. This will enable us to detect a 0.6 SD size effect at 90% power in serum 25OHD levels between placebo and 600 IU in UK-dwelling Brazilian populations and Brazilians living in Brazil. These study numbers of 40 subjects for the vitamin D group and n 40 for the placebo group includes a 20% drop-out rate factored in.

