7.0 Study Evaluation and Statistical Analysis

Statistical analysis will be undertaken with support from the University of Surrey statistical department. Data will be checked for normality using appropriate testing. Appropriate parametric/non-parametric analysis will be applied.

The database will be stored and analysed using SPSS ® version 13.0.

The descriptive analysis, including mean ± standard deviation, median and lower limit and higher will be held for all quantitative variables Data will be checked for normality using appropriate testing. Appropriate parametric/non-parametric analysis will be applied. Student t test or Mann-Whitney test, depending on the distribution of data, will be applied to evaluate differences between supplemented and placebo. For analysis between Brazil and UK groups an ANOVA test will be undertaken. Linear correlation, Pearson or Spearman, will be calculated in accordance with the presence / absence of normal distribution, respectively, between vitamin D intake, sun exposure, skin pigmentation and vitamin D serum concentration. Multiple linear regression analysis will be performed to determine the variants that influence blood concentrations of vitamin D. In order to determine whether supplemental response differs between genotypes, these will be separated into wild homozygotes, heterozygotes and homozygotes for the variant. In this approach, the results will be evaluated with the test ANOVA or Kruskal-Wallis, in cases of variables with normal distribution or not, respectively. To describe the relationship between food intake aspects and features biochemical independent of energy intake, intake values of nutrients of interest will be adjusted to energy in accordance with the method. Significance considered as standard will be 5%.

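### Body size is measured at baseline in both countries under a fixed 600 IU dose, but no inferential analysis or responder rule names it

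*Combined protocol and SAP*

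**What the plan says.** Section 3.0 gives all supplemented women one dose, 600 IU, with no scaling to body size. The eligibility criteria in 3.3 set no weight or BMI limit. The primary objective in 2.1 is the response to supplementation and "its influencing factors within and between Brazilian female adults" in the two countries.

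Section 4.1 lists anthropometrics and "Bioelectrical impedance analysis (BIA) for body composition" at both visits. Brazil also measures body composition by DEXA, at baseline only. Weight is not named in the visit lists. The term anthropometrics implies it, and the screening questionnaire records height and weight.

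Section 7.0 plans the following:

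- a t test or Mann-Whitney test between arms, without covariates
- ANOVA between countries
- correlations "between vitamin D intake, sun exposure, skin pigmentation and vitamin D serum concentration"
- a multiple linear regression on blood vitamin D concentration, with no predictor list
- ANOVA or Kruskal-Wallis by genotype
- descriptive statistics for all quantitative variables

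For the expression study, 48 participants are chosen, "encompassing the best and worst supplementation-responders in each group". Neither 3.0 nor 4.1 defines response or mentions body size in the selection.

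**The concern.** With a fixed dose, dose per kilogram varies with body weight. Taking 50 kg and 90 kg as illustrative weights, 600/50 = 12.0 IU/kg and 600/90 = 6.7 IU/kg, a 1.8-fold range. Body size is thus a natural candidate among the influencing factors in 2.1, and the data will already be in hand.

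Two things are at stake if body size is related to 25OHD response. An unadjusted arm test gives up some precision. More important, selecting women at the extremes of response would also select on size. Section 3.0 makes good versus poor responders the main expression comparison, and randomisation does not protect it. A difference in expression between the groups could then partly reflect body size.

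**Working it through.** **Inputs from the plan.** Section 3.1: "A total of 80 subjects (at 90% power) are required for recruitment into the 600 IU vitamin D group vs placebo group" in each country, 40 per arm, which "includes a 20% drop-out rate factored in", so 40 × 0.8 = 32 completers per arm. Target: "This will enable us to detect a 0.6 SD size effect at 90% power in serum 25OHD levels between placebo and 600 IU". Level, from 7.0: "Significance considered as standard will be 5" per cent; sidedness is not stated and two-sided is assumed.

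**Assumptions.** R² (share of outcome variance explained by baseline body size), r (correlation of body size with response) and the split of the 48 are not in the documents.

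**1. The plan's own figure.** Required n per arm = 2(1.960 + 1.282)²/0.6² = 58.4, so 59; with 20% dropout, 59/0.8 = 73.75, so 74. The stated 40 is not reproduced. Other readings also miss it, after dropout: one-sided 90% gives 60, two-sided 80% gives 55, one-sided 80% gives 44. Power at 32 per arm is Φ(0.6 × √(32/2) − 1.960) = Φ(0.44) = 67.0%. Using the t distribution it is 65.6%. That shortfall is a separate matter; 67.0% is only the starting value here.

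**2. Arm comparison with adjustment.** The residual SD becomes √(1 − R²), so power = Φ(2.4/√(1 − R²) − 1.960).

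| Assumed R² | SE reduction | Power at 32 per arm | n per arm for 90% |
|---|---|---|---|
| 0 | 0 | 67.0% | 59 |
| 0.02 | 1% | 67.9% | 58 |
| 0.05 | 2.5% | 69.2% | 56 |
| 0.10 | 5% | 71.6% | 53 |
| 0.20 | 11% | 76.5% | 47 |

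Reaching 90% at 32 per arm would need R² = 1 − 32 × 0.36/(2 × 3.242²) ≈ 0.45. Adjustment for body size does not repair the sample size at the values tried.

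**3. If size acts only in the supplemented arm.** Take unit variance in both arms, 1:1 allocation, slope r in the supplemented arm and 0 in placebo. The common slope is r/2. Residual variance is 1 − r² + r²/4 in the supplemented arm and 1 + r²/4 in placebo, averaging 1 − r²/4. For r = 0.2 to 0.5 the covariate removes 1% to about 6% of variance, not r² = 4% to 25%.

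**4. Responder groups.** Expected size gap = r × gap in mean standardised response between the extremes of 32 completers. In 200,000 simulated samples that response gap is 1.971 for 12 versus 12 and 2.779 for 6 versus 6. The first split follows if the 48 are divided by country (48/2/2 = 12), the second if by country and arm (48/4/2 = 6).

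| Assumed r | 12 vs 12 | 6 vs 6 |
|---|---|---|
| 0 | 0 | 0 |
| 0.2 | 0.39 SD | 0.56 SD |
| 0.3 | 0.59 SD | 0.83 SD |
| 0.4 | 0.79 SD | 1.11 SD |

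**The case against.** A reader might infer that body size enters no planned analysis at all. The documents do not support that. Descriptive statistics cover every quantitative variable, and the regression predictors are unlisted, so body size is unspecified, not excluded. Section 7.0 is not an exhaustive list either: baseline 25OHD is a stated response factor in 2.2 (vii) and H2, yet 7.0 does not name it. This stands, but the arm test and the correlations are specified, and both omit body size.

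A reader might also infer that a response model loses precision, by as much as 4 to 33% of effective sample size (1/(1 − r²) − 1 for r = 0.2 to 0.5). No response model is specified, and that gain applies to within-arm analyses. It does not carry over to the arm comparison, as step 3 shows.

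Nor do the documents show that responders will be sorted by size. They give no figure linking body size to 25OHD response, and the factors that section 1.0 lists for variable response leave body size out. The effect is conditional on r and on a split that the plan does not define, since its reference to both groups may mean countries or arms.

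Section 3.0 also compares each selected woman's expression before and after supplementation. This removes stable size-related differences within a woman. It mitigates the concern without ending it, because good versus poor remains the main comparison and change in expression may itself vary with size.

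Finally, ranking responders on size-adjusted residuals would change the question to who responds well given her size. It could remove genetic signal that acts through body fat, contrary to objective (viii) and H5. That objection stands, so selection should stay unadjusted.

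**Conclusion.** The concern holds in limited form. A baseline variable collected in both countries, and a natural candidate under the primary objective, is absent from every specified inferential analysis and from the responder selection. The omission does not bias the randomised comparison.

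The precision at stake there is modest: power of 67.9 to 76.5% instead of 67.0%, for an assumed R² of 0.02 to 0.20, and near the bottom of that range if size acts only in the supplemented arm. The more exposed part is the responder contrast, with a possible size gap of about 0.4 to 0.8 SD for assumed r of 0.2 to 0.4 and 12 versus 12. Both effects are zero if size and response are unrelated. The change is worth making because it improves a stated method at almost no cost; the documents do not establish that harm will occur.

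**What to change.** In 7.0, compare 25OHD between arms within each country by a linear model that includes baseline body weight or BIA fat mass. Choose one in advance and use the same method in both countries, so not DEXA. Use the baseline value only, since the final-visit value is post-randomisation. Name body size as an influencing factor under 2.1, with an arm-by-size term labelled exploratory, and list the regression predictors. State in 4.1 that anthropometrics include weight.

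For the expression study in 3.0 and 4.1, define response and the split of the 48, and keep the unadjusted ranking for selection. Tabulate baseline weight and fat mass by responder group, and repeat the good-versus-poor contrast adjusted for body size as a sensitivity analysis.

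The cost is a few lines of text and one or two model terms; no new data are needed. The interaction will be imprecise at about 32 completers per arm and should be reported as such.
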